### **5.2.2 Protocol pharmacology sampling visit schedule**

During protocol-specified clinic visits (described below and in Table 2), a blood sample will be collected from an arm vein for plasma/WB/RBC/DBS/PBMC isolation and safety laboratories. Hair will be cut from the scalp for comparison with other drug measures. Adverse events will be assessed. All protocol-specified clinic visits are detailed below. Each protocol-specified clinic visit will have a window of up to 10 days for sample collection.

#### **Clinic visit 1: Study entry visit (must be within 30 days after screening visit)**

- Medical, sexual, contraception, antenatal and vaccine history review
- Study blood work: WB, DBS, PBMC, plasma, (pre-drug for endogenous molecules such as nucleosides)
- Urine pregnancy test (urine  $\beta$  HCG)
- Study urine: (baseline endogenous molecules such as nucleosides)
- STI tests (CT, GC, syphilis, HSV-2)
- Blood work: hDNA for those who consent to drug transport gene testing
- Vaginal swab
- Dispense back up PrEP medication: subject home supply
- Dispense study dosing calendar
- DOT: Witness first PrEP dose

#### **Clinic visit 2: Week 1 Day/Dose 4 visit (for 2 doses per week group this will be 4 days since first dose):**

- Study Bloodwork: WB, DBS, PBMC, plasma
- Study urine
- Finger stick for DBS
- Cervicovaginal biopsy: **Random subset (50%) of cohort. These participants will not have a biopsy collected at the Week 1, Day 7 visit.**
- Vaginal swab
- Medical, sexual, contraception, antenatal and vaccine history review
- AE assessment
- Concomitant Medication Review
- DOT

#### **Clinic visit 3: Week 1 (Dose 7) visit:**

- Study bloodwork: WB, DBS, PBMC, plasma
- Study urine
- Finger stick for DBS

- Vaginal biopsy: **Random subset (50%) of cohort, comprising participants who did not have a biopsy collected at the Week 1, Day 4 visit**
- Vaginal swab
- Medical, sexual, contraception, antenatal and vaccine history review
- AE assessment
- Concomitant Medication Review
- DOT

**Clinic visit 4: Week 2 (Dose 14) visit:**

- Study bloodwork: WB, DBS, PBMC, plasma
- Study urine
- Medical, sexual, contraception, antenatal and vaccine history review
- AE assessment
- Concomitant Medication Review
- DOT

**Clinic visit 5: Week 3 (Dose 21) visit:**

- Study bloodwork: WB, DBS, plasma
- Study urine
- Medical, sexual, contraception, antenatal and vaccine history review
- AE assessment
- Concomitant Medication Review
- DOT

**Clinic visit 6: Week 4 (Dose 28) visit:**

- HIV rapid test
- Study bloodwork: WB, DBS, PBMC, plasma
- Study urine
- Finger stick for DBS
- Vaginal biopsy (all participants)
- Vaginal swab
- Hair collection
- Urine pregnancy test (urine  $\beta$  HCG)
- Medical, sexual, contraception, antenatal and vaccine history review
- AE assessment
- Concomitant Medication Review
- DOT

**Clinic visit 7: Week 5 (Dose 35) visit:**

- Study bloodwork: WB, DBS, PBMC, plasma
- Study urine
- Medical, sexual, contraception, antenatal and vaccine history review
- AE assessment
- Concomitant Medication Review
- DOT

**Clinic visit 8: Week 6 (Dose 42) visit:**

- Study bloodwork: WB, DBS, PBMC, plasma

- Medical, sexual, contraception, antenatal and vaccine history review
- AE assessment
- Concomitant Medication Review
- DOT
- Study urine

**Clinic visit 9: Week 7 (Dose 49) visit:**

- Study bloodwork: WB, DBS, PBMC, plasma
- Study urine
- Medical, sexual, contraception, antenatal and vaccine history review
- AE assessment
- Concomitant Medication Review
- DOT

**Clinic visit 10: Week 8 (Dose 56) visit:**

- HIV rapid test
- Urine pregnancy test (urine  $\beta$ HCG)
- Study bloodwork: WB, DBS, PBMC, plasma
- Finger stick for DBS
- Study urine
- Vaginal biopsy (all participants)
- Vaginal swab
- Hair collection
- Medical, sexual, contraception, antenatal and vaccine history review
- AE assessment
- Concomitant Medication Review
- DOT

**Clinic visit 11: Week 9 (Dose 63) visit:**

- Study bloodwork: WB, DBS, PBMC, plasma
- Study urine
- Medical, sexual, contraception, antenatal and vaccine history review
- AE assessment
- Concomitant Medication Review
- DOT

**Clinic visit 12: Week 10 Dose 70) visit:**

- HIV rapid test
- Study bloodwork: WB, DBS, PBMC, plasma
- Finger stick for DBS
- Study urine
- Safety Labs: Creatinine
- STI testing
- Medical, sexual, contraception, antenatal and vaccine history review
- AE assessment
- Concomitant Medication Review
- DOT

**Clinic visit 13: Post DOT PrEP visits (one week following dose cessation):** One visit at least 48 hours after the last DOT PrEP dose.

- Study bloodwork: WB, DBS, PBMC, plasma
- Study urine

**Clinic visit 14: Post DOT PrEP visits (Week 12-18):** One visit at least 14 days after visit above (i.e., the visit can occur any time between 2-8 weeks after the last DOT F/TAF PrEP which is between about week 12 and week 18 since enrollment)

- Study bloodwork: WB, DBS, PBMC, plasma
- Study urine
- Hair collection

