#### **4.2.1 Study product dispensation**

Two supplies of study drug will be dispensed for each participant. Both supplies will be dispensed in the original containers. Study personnel will be in possession of the main medication supply, which will be stored in a locked cabinet except during transportation to and from the directly observed dosing visits. This main supply will be enough for the entire 10-week DOT dosing period (enough medication to cover 10 weeks will be dispensed for the 70-84 day dosing window). Study personnel will record on the bottle the date that it is opened, and will ensure that opened bottles are used within 8 weeks. The locked cabinet will be in a temperature-controlled building, which is maintained at approximately 21°C. A second medication supply, a take-home supply, will be given to participants for non in-person dosing (video-streaming). Participants will be reminded to keep the medication in the original container with the desiccant, and to store it in a dry place with the cap tightly sealed. This take-home supply will be a maximum of one bottle of medication, with additional bottles given to participants when the current bottle is exhausted.

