## **5.2 Enrollment and Follow up Procedures**

Up to 54 evaluable HIV uninfected participants will be enrolled and followed up for 18 weeks: 10 weeks with DOT PrEP and up to 8 weeks for post drug kinetics sampling, with one visit at one week following dose cessation and an additional visit to occur between weeks 12 to 18. Enrollment must occur within 30 days of screening. An eligible participant who is unable to schedule a study entry visit within the 30-day screening window must be re-screened prior to entry into the study. All enrolments will be scheduled on specific days to avoid confusion in implementing the proposed dosing and sampling scheme. An adverse event questionnaire and medical and medication review will be conducted at each visit from study entry (enrollment) through week 10. Safety labs and vitals can be ordered as needed at any visit.

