##### ***Blood***

A blood sample will be obtained at protocol specified visits to process plasma, whole blood, DBS, and PBMCs. On a given study day blood collection, up to 21mL of blood for study bloodwork will be drawn with no planned timing relationship with dosing. The blood will be collected from an arm vein by trained clinic staff according to study site policies and procedures.

The schedule of protocol visits and procedures are outlined in Table 2.

Table 2: Schedule of protocol visit schedule and procedures.

Timeline (weeks)	Screening	Entry	DOT PrEP Period (weeks)											Post DOT Period	
			W1		W2	W3	W4	W5	W6	W7	W8	W9	W10	W11	W12-18
			Day 4	Day 7											
Clinic Visits #		1	2	3	4	5	6	7	8	9	10	11	12	13	14
Procedure															
Informed consent	x														
Medical, sexual, contraception, antenatal history review, vaccine history	x	x	x	x	x	x	x	x	x	x	x	x	x		
Physical exam a	x														
Dispense back up PrEP medication e		x													
Issue medical calendar		x													
AE assessment		x	x	x	x	x	x	x	x	x	x	x	x		
Safety Labs a,c	x	[x]											x		
Urine βHCG a	x	[x]						x				x			
HBS Ag	x														
HIV-1 rapid test a	x	[x]						x			x				
Hair collection							x			x		x			x
hDNA	x		x												
Study Bloodwork d (WB, plasma, DBS, PBMC)*PBMC is collected bi-weekly		x	x	x	x	x	x	x	x	x	x	x	x	x	x
Vaginal tissue f			x	x			x					x			
Vaginal swab		x	x	x			x				x		x		
DBS by fingerstick			x	x			x				x		x		
Study Urine d		x	x	x	x	x	x	x	x	x	x	x	x	x	x
Concomitant Medication Review	x	x	x	x	x	x	x	x	x	x	x	x	x		
STI testing (CT,GC, syphilis, HSV-2)		x											x		
DOT b		x	x	x	x	x	x	x	x	x	x	x	x		

[x] Indicated if screening occurred more 30 days before planned enrollment. The screen and entry visits must be ≤ 30 days apart.

a. Safety labs or vitals can be performed as needed at any time

b. DOT performed if applicable per randomization schedule

c. Protocol-specified safety labs include: CBC, HbAg, Creatinine clearance, in addition to monthly HIV testing and urine pregnancy tests.

d. Study Bloodwork: WB, DBS, PBMC, plasma and all available blood cell types; Study Urine: endogenous molecules such as nucleosides.

\*PBMC is collected bi-weekly (baseline, week 2, 4, 6, 8, 10)

e. Study medications will be dispensed as described

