## **6.7 Discontinuation of Study Medication**

Subjects may withdraw from the study at any time. Any participant who prematurely discontinues study medication (for toxicity or pregnancy) should be followed for study duration. Subjects who become pregnant or who acquire HIV infection will have study drug discontinued but will be followed to determine the pregnancy outcome.

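### No urine pregnancy test is scheduled after the last dose; testing at visit 14, and listing the test at visit 12, would close a small safety gap cheaply

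*Combined protocol and SAP*

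**What the plan says.** After screening, the section 5.2.2 lists include a urine pregnancy test at visit 1 (entry), visit 6 (week 4) and visit 10 (week 8, day 56), where the item reads "Urine pregnancy test (urine" β-HCG). Visits 11 to 14 list none. Visit 12, at week 10, does list "HIV rapid test" and "Safety Labs: Creatinine", along with STI testing and study urine. For visit 14, the last visit, section 5.2.2 says that "the visit can occur any time between 2-8 weeks after the last DOT F/TAF PrEP".

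Dosing goes on after day 56. Section 4.2.1 says that "enough medication to cover 10 weeks will be dispensed for the 70-84 day dosing window".

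Other text is less specific. Table 2, footnote c, describes the safety labs as being "in addition to monthly HIV testing and urine pregnancy tests", without naming visits. Section 8.5 puts a monthly urine pregnancy test in a bracketed list of labs done at entry and at 10 weeks.

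On clinical review, section 5.2 states: "An adverse event questionnaire and medical and medication review will be conducted at each visit from study entry (enrollment) through week 10". Visits 13 and 14 list bloodwork and urine, plus hair at visit 14. They list no history or adverse-event review.

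On consequences, section 6.7 says that women who become pregnant "will have study drug discontinued but will be followed to determine the pregnancy outcome". Section 6.6 counts a birth defect as a serious adverse event. Section 6.9 ends SAE reporting when the woman's own follow-up ends. Section 3.8 replaces women who become pregnant and keeps them in follow-up to the end of their scheduled visits.

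**The concern.** The promise to follow a pregnancy to its outcome takes effect only once the pregnancy is known. A woman who conceives in the last weeks of dosing can test negative, or be too early to test positive, at week 8. She then completes visits 11 to 14 exactly as listed without being tested again. If she has not recognised the pregnancy by visit 14, her follow-up closes, and SAE reporting closes with it. Any later birth outcome of a pregnancy exposed to study drug is then lost.

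Safety is the first primary objective, and infant exposure already matters to the protocol: section 8.5 bars breastfeeding on that ground. What is at stake is completeness of safety follow-up in a rare case. Little dosing would be prevented, because most of the gain comes from a test after dosing has stopped.

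**Working it through.** **1. The plan's own timing.** Ten weeks of dosing is 10 × 7 = day 70. The outer window of 84 days is 12 weeks. Visit 14 falls 2 to 8 weeks after the last dose, so 10 + 2 = week 12 to 10 + 8 = week 18. This reproduces the week 12-18 stated in section 5.2.2.

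**2. Dosing days after the last listed test.**
- Dosing to day 70: 70 − 56 = 14 days, 14/70 = 20%.
- Dosing to day 84: 84 − 56 = 28 days, 28/84 = 33%.

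**3. Allowing for a detection lag.** Assume that a urine test turns positive L = 1 to 3 weeks after conception (not in the documents). Dosing weeks in which a conception cannot show at week 8 are (end of dosing − 8) + L:
- Ten weeks of dosing: 2 + 1 = 3 to 2 + 3 = 5 weeks.
- Twelve weeks of dosing: 4 + 1 = 5 to 4 + 3 = 7 weeks.

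**4. Expected conceptions in that gap.** Assume r = 2 to 10 pregnancies per 100 woman-years (the protocol gives no rate). Expected number E = 54 × weeks/52.18 × r, and P(at least one) = 1 − exp(−E).

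| Case | Woman-years | r | E | P(at least one) |
|---|---|---|---|---|
| 10 weeks, L = 1 | 54 × 3/52.18 = 3.10 | 0.02 | 0.06 | 6% |
| 10 weeks, L = 3 | 54 × 5/52.18 = 5.17 | 0.10 | 0.52 | 40% |
| All dose to day 84, L = 1 | 54 × 5/52.18 = 5.17 | 0.02 | 0.10 | 10% |
| All dose to day 84, L = 3 | 54 × 7/52.18 = 7.24 | 0.10 | 0.72 | 52% |

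**5. What an added test leaves uncovered.**
- Visit 12 only, on the last dosing day: L weeks remain, that is 1, 2 or 3.
- Visit 14 only, d weeks after the last dose: max(0, L − d). At d = 2 this is 0, 0 and 1 week for L = 1, 2 and 3. At d of 3 or more it is 0.

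Visit 14 therefore does nearly all the work. Visit 12 brings earlier detection and covers women who miss visit 14.

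**6. Effect on the benchmarks.** Section 1.1.4 cites a 30-40% reduction in TFV-DP in pregnancy, from FTC/TDF data. Suppose that one woman in an arm of 18 had her late samples fully reduced by 40%, and that concentrations are otherwise similar. The arm mean at those visits would move by 40%/18 = 2.2%, against a precision target of 15% in section 7.4. Even this overstates the effect, because the roughly 17-day half-life of TFV-DP in DBS (section 5.2.1) means that a recent change would show only in part.

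**The case against.** The strongest reply is that the protocol already covers most of this. Tests at entry, week 4 and week 8 are monthly for a 10-week course. Section 8.5 can be read as placing a test at week 10. Visits 11 and 12 both include contraception and antenatal history and adverse-event review, which can prompt a test. Testing as needed is allowed, women have a 24-hour number (section 6.3), effective contraception is required (section 3.1), and women planning pregnancy are excluded (section 3.2).

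Much of this stands. It lowers the risk and makes the visit 12 part of the fix largely a matter of bringing section 5.2.2 into line with section 8.5. It does not supply a test after the last dose. If section 8.5 does mean week 10, conceptions in the last 1 to 3 dosing weeks still cannot show. I do not rely on the column marks in Table 2, because they may have shifted in text extraction. A mark at week 9 would still precede the last dose and leave (10 − 9) + L = 2 to 4 weeks. As-needed testing depends on someone suspecting a pregnancy, and visits 13 and 14 list no review that would raise the question.

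Four stronger readings are tempting, and the documents do not support them:
- *Sections 3.8 and 6.7 contradict each other.* Section 3.8 does not say that follow-up stops at the last scheduled visit, and section 6.7 adds follow-up to outcome. Both can hold, so the need is for clarification.
- *The week 10 HIV test shows that the pregnancy test was forgotten.* The HIV test has its own basis: section 8.5 requires it at the end of dosing, and section 4.8 cites resistance.
- *The benchmarks would be biased.* Step 6 shows a negligible effect even in an unfavourable case.
- *A woman with complete dosing and PK data should not be replaced after a late positive.* That would override section 3.8 and the target of non-pregnant evaluable women in section 2.5.

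**Conclusion.** The gap is real and narrow. No part of the protocol schedules a pregnancy test after the last dose, and the visit lists stop testing at day 56. A conception late in dosing can go unrecognised and fall outside the outcome follow-up and birth-defect reporting that the protocol intends.

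Fewer than one case is expected: about 0.06-0.52 among 54 women with 10 weeks of dosing, or 0.10-0.72 if every woman dosed to day 84. These figures rest on the assumed lag and pregnancy rate. The upper ends combine the longest lag with the highest rate, in women who are required to use contraception, so there may well be no case at all. The absence of a scheduled post-dosing test does not depend on those assumptions. This is a low-probability patient-safety improvement that is worth making because it costs so little. It is not a flaw in the PK design or a breach of the protocol's own monthly testing.

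**What to change.** 1. **Visit 14:** add a same-day urine pregnancy test with counselling on the result. Urine is already collected there, but section 5.2.3.1 earmarks it for future testing, so the schedule and consent wording should name the same-day use.
2. **Visit 12:** list the test in section 5.2.2 and align Table 2, so that both agree with section 8.5.
3. **Section 3.8:** add that a pregnancy is followed to its outcome, as section 6.7 states.
4. **Leave alone:** keep the replacement rule in section 3.8 as it is. No PK sensitivity analysis is needed on this account.

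Cost: 54 × 2 = 108 urine tests. Section 3.8 caps replacements at 20%, and 0.20 × 54 = 10.8, so at most 10; the ceiling is (54 + 10) × 2 = 128 tests. There is no new visit or invasive procedure. Rarely, a late positive would mean follow-up to outcome beyond the last visit, which section 6.7 already promises, or a replacement under section 3.8, with a further 10 weeks of observed dosing and biopsies for the new participant.

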### **5.2.3 Clinical Evaluations/Procedures**

Scheduled protocol visits and procedures are outlined in Table 5. At the screening visit a qualified study clinician will perform a history and physical for each participant. A complete medication history will be obtained including all drug allergies, immunization history, prescription, over the counter, herbal treatments, contraception use history. Vital signs will include height, weight, blood pressure, pulse, respiratory rate and temperature.

#### **5.2.3.1 Specimen collection**

All pharmacokinetic samples must be collected as per the protocol-specified schedule. Each protocol-specified pharmacokinetic sampling visit will have a window of up to 10 days for sample collection. The pharmacokinetic samples will be collected as follows:

##### ***Blood***

A blood sample will be obtained at protocol specified visits to process plasma, whole blood, DBS, and PBMCs. On a given study day blood collection, up to 21mL of blood for study bloodwork will be drawn with no planned timing relationship with dosing. The blood will be collected from an arm vein by trained clinic staff according to study site policies and procedures.

The schedule of protocol visits and procedures are outlined in Table 2.

Table 2: Schedule of protocol visit schedule and procedures.

Timeline (weeks)	Screening	Entry	DOT PrEP Period (weeks)											Post DOT Period	
			W1		W2	W3	W4	W5	W6	W7	W8	W9	W10	W11	W12-18
			Day 4	Day 7											
Clinic Visits #		1	2	3	4	5	6	7	8	9	10	11	12	13	14
Procedure															
Informed consent	x														
Medical, sexual, contraception, antenatal history review, vaccine history	x	x	x	x	x	x	x	x	x	x	x	x	x		
Physical exam a	x														
Dispense back up PrEP medication e		x													
Issue medical calendar		x													
AE assessment		x	x	x	x	x	x	x	x	x	x	x	x		
Safety Labs a,c	x	[x]											x		
Urine βHCG a	x	[x]						x				x			
HBS Ag	x														
HIV-1 rapid test a	x	[x]						x			x				
Hair collection							x			x		x			x
hDNA	x		x												
Study Bloodwork d (WB, plasma, DBS, PBMC)*PBMC is collected bi-weekly		x	x	x	x	x	x	x	x	x	x	x	x	x	x
Vaginal tissue f			x	x			x					x			
Vaginal swab		x	x	x			x				x		x		
DBS by fingerstick			x	x			x				x		x		
Study Urine d		x	x	x	x	x	x	x	x	x	x	x	x	x	x
Concomitant Medication Review	x	x	x	x	x	x	x	x	x	x	x	x	x		
STI testing (CT,GC, syphilis, HSV-2)		x											x		
DOT b		x	x	x	x	x	x	x	x	x	x	x	x		

[x] Indicated if screening occurred more 30 days before planned enrollment. The screen and entry visits must be ≤ 30 days apart.

a. Safety labs or vitals can be performed as needed at any time

b. DOT performed if applicable per randomization schedule

c. Protocol-specified safety labs include: CBC, HbAg, Creatinine clearance, in addition to monthly HIV testing and urine pregnancy tests.

d. Study Bloodwork: WB, DBS, PBMC, plasma and all available blood cell types; Study Urine: endogenous molecules such as nucleosides.

\*PBMC is collected bi-weekly (baseline, week 2, 4, 6, 8, 10)

e. Study medications will be dispensed as described

f. Random subset (50%) on day 4 and the remaining subset (50%) on day 7. All participants will have week 4 and week 8 sample.

### Vaginal swab and tissue

Vaginal swabs and a vaginal tissue sample will be collected. Vaginal biopsies will be taken with 2.3 x 4.2-mm Tischler gold-plated gynecological forceps.

**Justification for vaginal tissue sampling:** Vaginal mucosa is a tissue of great relevance to the acquisition of HIV infection for cisgender women. The planned sampling schedule will help to define early drug kinetics and how soon drugs accumulate in vaginal tissue following PrEP initiation the week until steady state is reached. To minimize risk associated with this procedure and the burden on study participants, we will ensure each participant will have only one biopsy in a 4 week-period by sampling separate participants at days 4 and 7 of Week 1. Thus, in week 1, half of the participants will be biopsied on day 4, and half will be biopsied on day 7. All participants will provide tissue samples at week 4 and 8.

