#### 7.5 Randomization and Blinding Procedures

The study design will be an open-label, randomized study with three arms. The randomization assignment will be made at enrollment if the participant is eligible and agrees to enroll. Randomization will be according to the PrEP dosing frequency and vaginal tissue collection plan (either sampling day 4 or day 7) 1:1:1 fashion programmed by the study statistician and generated from REDcap.

The allocation of participants for the 3 study arms will be the following:

	2 doses per week	4 doses per week	7 doses per week	Total
Total	18	18	18	54

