### **Risks from vaginal biopsy**

Vaginal tissue biopsy is an invasive procedure and we have carefully considered the risk involved including some discomfort, pain and potential for bleeding and burden on cisgender women. Sampling vaginal tissue is important to fully characterize HIV protection in cisgender women since it is a tissue of relevance to the acquisition of HIV infection for cisgender women and will help to define early drug kinetics and how soon drugs accumulate in vaginal tissue from PrEP initiation until steady state. To minimize risks, we have carefully considered sampling schedule to minimize risk associated with this procedure and burden on cisgender women: Each participant will provide only one biopsy in a 4-week period by sampling unique cisgender women (i.e., for each planned tissue sampling visit different cisgender women will be sampled at day 4 and day 7). All participants will provide a vaginal tissue sample for week 4 and 8.

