### **Protection of risk related to vaginal tissue biopsy**

We have also carefully considered our sampling schedule to minimize risk associated with vaginal tissue biopsy and burden on cisgender women and will take the following measures: 1) Only low HIV risk non-pregnant cisgender women will provide vaginal tissue samples 2) Each participant will provide only one

biopsy in a 4-week period. We will sample cisgender women as two separate groups during the first week, i.e. half of participants on day 1 and the other half on day 7. This will ensure sufficient time between the week 1 and week 4 sample. All participants will provide vaginal tissues samples during weeks 4 and 8. Participants will be counseled to avoid sex in ~7 days after biopsy.

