## **9 LABORATORY SPECIMENS AND BIOHAZARD CONTAINMENT**

### **9.1 Laboratory evaluations and specimen collections**

The following safety and monitoring laboratories will be collected at regular intervals during the study as described above: complete hematology panels, pregnancy tests (urine), HIV tests (rapid or regular), serum creatinine (estimated creatinine clearance), and HBV surface antigen test. The HIV and HBV tests will be used to screen HIV-negative volunteers for inclusion in the study. The tests are provided according to established laboratory procedures at site. These clinical laboratories/sites conform to CAP and/or CLIA-regulations, and the results will be posted to the participant's medical record as positive or negative.

All pharmacokinetics samples will be collected, processed, and stored according to standard operating procedures developed by the Colorado Antiviral Pharmacology Laboratory. On each pharmacokinetics sample visit day, samples will be collected without regard to the dosing time within each day (i.e., sampling is at convenience times rather than troughs). The only exception will be at the entry visit, where samples are to be obtained pre-dose. We will take a comprehensive approach to establish benchmark adherence-concentration thresholds for cisgender women using daily DOT TAF/FTC PrEP by collecting samples for pharmacokinetic measurements in multiple biologic matrices: plasma, whole blood, DBS, PBMCs, vaginal swabs, and vaginal tissue and by archiving urine and hair samples. All cisgender women will contribute to this comprehensive assessment during the study participation duration of up to 18 weeks (10 weeks of DOT PrEP and 8 weeks post DOT PrEP for post drug kinetics). Within each group, we will collect pharmacokinetic samples (plasma, whole blood, DBS, PBMCs) to measure the respective concentrations of TAF/FTC moieties at day 4 and weekly up to 8 weeks with daily DOT PrEP dosing and vaginal tissue at day 4, week 1, 4, and 8.

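### The safeguard of one biopsy per four weeks does not match the schedule: the week 1 and week 4 biopsies are nominally 24 or 21 days apart

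*Combined protocol and SAP*

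**What the plan says.** The limit appears in three places, each time as a protection for participants.

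- Section 5.2.3.1 (Vaginal swab and tissue): "each participant will have only one biopsy in a 4 week-period by sampling separate participants at days 4 and 7" of week 1.
- Section 8.4 (Risks from vaginal biopsy): "Each participant will provide only one biopsy in a 4-week period", to be achieved "by sampling unique cisgender women (i.e., for each planned tissue sampling visit different cisgender women will be sampled at day 4 and day 7").
- Section 8.5 (Protection of risk related to vaginal tissue biopsy): the same limit, followed by the two-group split, given here as "half of participants on day 1 and the other half on day 7". It adds that this leaves enough time between the week 1 and week 4 samples.

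The schedule is consistent elsewhere. Section 5.2.2 puts the first biopsy at clinic visit 2 (day 4) for one random half and at clinic visit 3 (day 7) for the other. It then lists a biopsy for all participants at clinic visits 6 (week 4, dose 28) and 10 (week 8, dose 56). Table 2, footnote f, confirms: "All participants will have week 4 and week 8 sample". Section 9.1 lists "vaginal tissue at day 4, week 1, 4, and 8", and Section 7.5 randomises the "vaginal tissue collection plan (either sampling day 4 or day 7").

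Sections 5.2.2 and 5.2.3.1 give each visit a sampling window of up to 10 days. They do not say whether it runs early, late or both, and they make no exception for biopsy visits.

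**The concern.** The three sections offer the day 4/day 7 split as the means of keeping a woman's biopsies four weeks apart. The split only decides which week 1 visit carries her first biopsy. It cannot lengthen the interval to the week 4 biopsy, which everyone has on the same nominal day.

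What is at stake is the accuracy of a stated safeguard for an invasive procedure, and its use in scheduling. The four-week sentence is the only numeric limit on biopsy spacing in this protocol. If the nominal days already fall short of it, the text does not tell the site how close two biopsies may come when visits shift within the window.

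**Working it through.** **Inputs.** First biopsy on day 4 or day 7 (Section 5.2.2, visits 2 and 3; Table 2, footnote f). Second on day 28 and third on day 56 (visits 6 and 10). The dose 28 and dose 56 labels are read as study days in all arms, since the 2- and 4-dose arms will have had only 4 × 2 = 8 and 4 × 4 = 16 doses by week 4. Stated limit: 4 × 7 = 28 days. Planned number of women: 54, split 50:50.

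**Nominal gaps**

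| Interval | Day-4 half | Day-7 half |
|---|---|---|
| First to second | 28 − 4 = 24 days | 28 − 7 = 21 days |
| Shortfall against 28 | 4 days | 7 days |
| Second to third | 56 − 28 = 28 days | 56 − 28 = 28 days |

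The stated four weeks is reproduced for the second interval only.

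**How many intervals.** 54 × 2 = 108 planned intervals. The 54 first intervals (27 at 24 days, 27 at 21 days) are nominally short; the 54 second intervals are not.

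**Sensitivity to day counting.** Shifting the count by one day at either end gives 23–25 and 20–22 days. Taking the day 1 of Section 8.5 literally gives 28 − 1 = 27 days. All are below 28.

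**Fixed four-week blocks.** Days 1–28 contain two biopsies for every woman. Blocks counted from day 0 (0–27, 28–55, 56 onward) contain one each, but the first two biopsies are still 21 or 24 days apart.

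**Effect of the window, assuming it runs late only (0 to +10 days)**

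- Day-4 half: first gap from 28 − 14 = 14 to 38 − 4 = 34 days.
- Day-7 half: first gap from 28 − 17 = 11 to 38 − 7 = 31 days.
- After an on-time first biopsy, 28 days is reached if the second falls on days 32–38 (4 + 28 = 32) or 35–38 (7 + 28 = 35). The third is then due from day 60 or 63, inside a window ending on day 66.
- It is out of reach if the first biopsy is more than 38 − 32 = 6 or 38 − 35 = 3 days late.

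The short extremes strain the week 1 visit label and are illustrative only. A modest shift makes the same point: a day-7 biopsy one day late, with week 4 on time, gives 28 − 8 = 20 days.

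**Feasibility of a 21-day floor.** The earliest second biopsy is day 4 + 21 = 25 or 7 + 21 = 28. If the first is d days late, it is 25 + d or 28 + d. In the day-7 half the second therefore has to be at least as late as the first, so one permitted day always remains if both visits share the same window (at the late-only extreme, 17 + 21 = 38). Week 8 can stay on day 56 if the second biopsy is by 56 − 21 = 35.

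**The case against.** Four objections have weight.

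1. A reader might infer that no interpretation of the limit fits the schedule. That goes too far. Section 6.9 sets enrollment as day 0, and blocks counted from day 0 hold one biopsy each. It is a poor reading, because Section 8.5 is concerned with the time between the week 1 and week 4 samples, which such blocks do not protect. It does exist, however.

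2. A reader might infer that 28 days cannot be achieved, or that the limit is useless in practice. The documents do not support this. If the window runs late, the site can reach 28 days with a second biopsy on days 32–38 or 35–38. What stands is that the nominal days miss the limit and nothing makes the week 4 biopsy conditional on 28 days having passed.

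3. A reader might infer that the site has no spacing rule at all. Sections 6.10 and 10.3 refer to a study-specific procedures manual that is not available here, so the statement can be made only of this protocol.

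4. A reader might infer harm, or that participants were misinformed. Neither is shown. Both gaps exceed the only post-biopsy interval given, seven days of abstinence (Section 3.1). The actual biopsy days are printed beside the statement in all three sections, apart from the day 1 slip in Section 8.5, and the consent pages are not available.

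These points limit the concern but do not remove the mismatch between the stated limit and the nominal schedule.

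**Conclusion.** The point holds as a minor inconsistency in the safety wording. On nominal days, every woman's first interval is shorter than the four weeks stated: 24 days in the day-4 half and 21 days in the day-7 half. Only week 4 to week 8 is 28 days. The split prevents two biopsies in week 1 and does no more than that for spacing. The visit window may bring some women to 28 days and others below 21, so the limit is not ensured.

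This rests on reading weeks 4 and 8 as days 28 and 56 and the limit as time between successive biopsies. The window results also assume that it runs late only. Endpoints, sample size and estimates are unaffected.

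**What to change.** In Sections 5.2.3.1, 8.4 and 8.5, replace the four-week statement with: *nominally 24 or 21 days between the week 1 and week 4 biopsies and nominally 28 days between week 4 and week 8; the visit window may not be used to bring two biopsies in the same woman closer than 21 days.* In Section 8.5, correct day 1 to day 4. No biopsy day moves and no procedure is added. The 21-day floor is the shortest nominal gap, not a documented healing interval; if the investigators have a clinical basis for another minimum, it should be used and cited.

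Costs:

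- The stated interval is less favourable.
- Scheduling is tighter. After an on-time first biopsy, week 4 can be at most 28 − 25 = 3 days early in the day-4 half and not early at all in the day-7 half.
- There is a small risk of missed tissue samples. Section 9.1 counts vaginal tissue among the pharmacokinetic matrices, and Section 3.8 replaces women who miss a pharmacokinetic sample, up to 20% of 54 (10.8, so 10 women).

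The alternative is to keep 28 days and move the second biopsy to day 32 or 35 and the third to day 60 or 63 at the earliest. A late-running window may already allow these days, but it would shift the planned tissue time points, so the wording change is preferred.
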